
• doesn't have a well visit scheduled in the next 45 days	
• doesn't have a well visit scheduled in the next 45 days

 • has not had a well child visit > 365 days • have English and/or Spanish as preferred language 	
 • has not had a well child visit in 365 days • have English and/or Spanish as preferred language
---	---

Factors under study (levels):

Personal Contacts (12-14 month & 4-year-olds) Trial:

Number of automated messages sent prior to any personal contact attempts (1 vs. 2)
Number of personal contact attempts made by medical assistant (0 vs. 1)

	1 automated message sent	2 automated messages sent
0 personal contact attempt		
1 personal contact attempt		

MyChart Trial:

Families enrolled in MyChart will be selected and randomized into the following groups:

	no message	1 MyChart message sent	2 MyChart messages (e.g. Mon and Thurs)
Low Tailored Message			
High Tailored Message			

Number of messages (0 vs. 1 vs. 2); Type of messages (low tailored message with name only vs. high tailored message with date of last WCC and age included)

Televox (age 6-11yo) Trial:

Patients will be randomized into the following three groups. Patients with MyChart are excluded:

no message	Low tailored Message 2 automated standard messages sent (e.g. Thu, Fri)	High Tailored Message 2 automated tailored messages sent (e.g. Thu, Fri)
-------------------	---	--

Televox (age 12-17yo) Trial:

Patients will be randomized into the following three groups:

no message	Low Tailored Message 2 automated tailored messages sent (e.g. Thu, Fri)	COVID Tailored Message 2 automated messages sent (e.g. Thu, Fri)
-------------------	---	--

Automated Message: Parents indicate their preferred mode of reminder (e.g. call or text message) when they schedule appointments. Cincinnati Children's uses a HIPAA compliant platform called TeleVox to send automated calls and text reminders to parents according to their preferences which are recorded in the Electronic Health Record (EHR).

Here is the script for **low tailored automated messages** that will be sent via call or text:

Clinic	Message 1*	Message 2*

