PPC	Hi, this is [Staff First Name] from PPC. [Pt first name] is due for a check up. I'll call in a day or two to help schedule that appointment or you can walk in today to have your child seen! You can also call [contact], option 1 to schedule.	Hi, this is [First Name] from PPC. I noticed that [Child's First Name] is due for a check up. Can I schedule that for your right now? Alternate script for leaving a voice message: Hi, this is [First Name] from PPC. I noticed that [Child's First Name] is due for a check up. Sorry I missed you. Please call [contact], option 1 to schedule your appointment or walk in today to have your child seen.

*Scripts have been translated into Spanish versions by Interpreter Services

Response variables (outcomes):

- Appointment **was scheduled** within 2 weeks of intervention (Y/N) (date of actual appointment may be greater than 2 weeks from intervention)
- Appointment **was completed** within 8 weeks of intervention (Y/N). Appointment completed within 8 weeks of randomization will be used for group who does not receive any intervention.
- (Primary Outcome) Receipt of MMR by 15 months of age or receipt of 2nd MMR dose by 3 months after randomization (Y/N)
- Receipt of 1st COVID vaccination (ages 12-17 years) within 8 weeks of first intervention (Y/N)
- Family member receipt of COVID vaccination in our health system within 8 weeks of first intervention

Blocking: (controlling for factors that might influence the outcome)

- Age (12-14 months, 4 years)
- Clinic location (PPC, HPC, FPC)

Personal Contacts (12-14 months & 4-year-olds) Trial:

Randomization: Eligible patient will be identified by running a report in the electronic health record (EHR). We will run this report, stratified by clinic location, and randomly assign patients into one of the four groups created by our 2 X 2 design. Groups will receive their assigned intervention in one of four successive weeks with the sequence randomly assigned (see table below).

Replication: We will conduct a total of 3 trials, repeating the randomization procedure every 4 weeks to identify children who become eligible: Weeks 1-4 = trial #1, weeks 5-8 = trial #2, weeks 9-12 = trial #3.

Outreach Methods Study Protocol & SAP

Version 1.1, 1/14/22

	1 automated message sent	2 automated messages sent
0 personal contact attempt	Message sent on Thu (weeks 3, 5, 10)	Message sent on Thu & Fri (weeks 4, 6, 12)

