1 personal contact attempt	Above plus attempt Mon – Fri of following week (weeks 2, 7, 11)	Above plus attempt Mon – Fri of following week (weeks 1, 8, 9)

MyChart and Televox Trials (6-17 years old):

Randomization: Eligible patients will be identified by running a report in the electronic health record (EHR). We will run this report, stratified by clinic location, and randomly assign patients into one of the study groups as described above. Groups will receive their assigned intervention in one of four successive weeks with the sequence randomly assigned (see table below).

We will randomize children who are eligible and implement interventions for each trial : Weeks 1-3 = Televox Trial 12-17yo, Weeks 4-7 = Televox Trial 6-11yo, Weeks 8-10 = MyChart Trial.

MyChart Trial:

	no message	1 MyChart message sent	2 MyChart messages (e.g. Mon and Thurs)
Standard Message	No intervention	Week A	Week B
Tailored Message		Week A	Week B

Televox (6-11yo) Trial:

no message	Low Tailored Message 2 automated standard messages sent (e.g. Thu, Fri) (weeks C, C)	High Tailored Message 2 automated tailored messages sent (e.g. Thu, Fri) (weeks D, D)
-------------------	--	---

Televox (12-17yo) Trial:

no message	Low Tailored Message 2 automated tailored messages sent (e.g. Thu, Fri) (week A)	COVID Tailored Message 2 automated messages sent (e.g. Thu, Fri) (week B)
-------------------	--	---

Of note, automated messages and/or personal contact attempts will not be completed if the parent schedules an appointment after being randomized but before receiving the intervention.

Covariates for logistic regression: (factors that might influence the outcome if not balanced across groups)

1. Child age at the time of randomization (rationale: visits are less frequent for children age 4 years)
2. Parent preference for call vs. text mode of contact (rationale: calls may be more likely to get blocked than texts)
3. Parent with activated MyChart account (Y/N) (rationale: not dependent on calling scheduling center to make appointment)

4. Access to appointment: Number of days to 3rd next available appointment at patient's clinic at time their first automated message is sent
5. Patient receipt of any past immunizations (Y/N) (rationale: vaccine refusing parents will be unlikely to change even if they return for well child check)
6. School-age vs. adolescent patient age (rationale: adolescents less likely to get yearly check-ups)
7. Historical no-show rate

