2.3.2 Primary outcome analysis

Primary outcome: Adolescent well-care visit completed within 8 weeks of first message sent or date of randomization for the control group.

- Appointment completed (yes or no) based on electronic health record documentation

For the primary outcome, we will use a logistic regression model to examine appointment completion within 8 weeks among the three randomized groups. If participants differ in potential covariates across treatment groups, we will conduct additional analyses adjusted for these variables.

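### Adolescents with MyChart can be randomized a second time, in the MyChart trial, before their 12-17 Televox outcome window closes; exposure differs by arm, in a direction the plan does not fix

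*Combined protocol and SAP*

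**What the plan says.** In the protocol's list of factors under study, the 6-11 Televox trial carries the line "Patients with MyChart are excluded". The 12-17 Televox trial, described directly below it, says only "Patients will be randomized into the following three groups". Entry to the MyChart trial reads "Families enrolled in MyChart will be selected and randomized into the following groups". The shared randomization heading for these trials gives the ages as 6 to 17, and the covariate list contrasts school-age with adolescent patients, so adolescents are in the MyChart pool. No section bars a child randomized in one trial from entering another.

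The calendar is "Weeks 1-3 = Televox Trial 12-17yo, Weeks 4-7 = Televox Trial 6-11yo, Weeks 8-10 = MyChart Trial". Within a trial, the order in which groups are messaged is randomly assigned, and the tables label the weeks only by letter.

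The SAP's primary outcome (section 2.3.2) is "Adolescent well-care visit completed within 8 weeks of first message sent or date of randomization for the control group". The protocol's outcome list uses the same anchor for the no-message arm: "Appointment completed within 8 weeks of randomization will be used for group who does not receive any intervention".

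Eligibility at 12-17 requires no well visit in the past 365 days and none scheduled in the next 45 days.

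**The concern.** An 8-week window opened in weeks 1-3 is still partly open in weeks 8-10. A visit or vaccination prompted by a MyChart message in that period would be counted for the Televox arm to which the adolescent was first assigned.

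The exposure is not equal between arms, for two reasons. The control clock starts at randomization and the message clocks start later, so message-arm windows close later. Against that, MyChart entry depends on not having booked or attended, so more of the control arm is left to be messaged.

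The contrast at stake is standard versus COVID message, where both the protocol and the SAP plan on a 10-point difference. The SAP would not reveal the problem: its baseline list (section 2.3.1) omits MyChart status, and it has no rule for later outreach.

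**Working it through.** **Plan's own figure.** For 30% versus 40%, two-sided alpha 0.05, 80% power, pooled variance and no continuity correction, n = 356 per group and 3 × 356 = 1068. This matches the protocol.

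**Window overlap.** Assumptions: Monday of week 1 is day 1; the window is 56 days; control is randomized on day 1; Televox first messages go out on a Thursday; MyChart first messages go out on a Monday (days 50, 57 and 64 for weeks 8, 9 and 10).

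| Arm | Window closes | Days open after MyChart in week 8 / 9 / 10 |
|---|---|---|
| Control | 1 + 56 = day 57 | 7 / 0 / 0 |
| First message week 1 | 4 + 56 = day 60 | 10 / 3 / 0 |
| First message week 2 | 11 + 56 = day 67 | 17 / 10 / 3 |
| First message week 3 | 18 + 56 = day 74 | 24 / 17 / 10 |

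If control were randomized in week 2 or 3, its week-8 overlap would be 14 or 21 days. The last window closes on Thursday of week 11 (day 74), so a start in week 12 (day 78) gives no overlap.

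**Children left to message.** On the protocol's assumed completion rates (2%, 30%, 40%), 98% of control, 70% of standard and 60% of COVID adolescents have no completed visit. Four of five MyChart groups are messaged (80%).

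**MyChart share s.** The stated pools are 1000 (MyChart), 2500 (6-11) and 1100 (12-17). Assume an equal share at both ages.
- If the 2500 includes MyChart families: s = 1000 / (2500 + 1100) = 28%.
- If it excludes them: s × [2500 / (1 − s) + 1100] = 1000, so s = 23%.

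**Added points per arm, response spread evenly.** The mean MyChart response is (10 + 20 + 20 + 30) / 4 = 20%, or 18 points above the 2% no-message rate.

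Added = s × (1 − p) × 0.8 × 18 × (days open / 56)

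With s = 0.28 and MyChart in week 8:
- Standard in week 3: 0.28 × 0.70 × 0.8 × 18 × 24/56 = 1.21. COVID in week 1: 0.28 × 0.60 × 0.8 × 18 × 10/56 = 0.43. Shift −0.8.
- Standard in week 1: 0.50. COVID in week 3: 1.04. Shift +0.5.
- Arms in adjacent weeks: shift within ±0.5.
- Control: 0.28 × 0.98 × 0.8 × 18 × 7/56 = 0.49. Standard versus control moves from 28 to between 28.0 and 28.7 points.

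The COVID-versus-standard contrast therefore lies between 9.2 and 10.5 points, with power at 356 per group between 73% and 84%. With the SAP's rates (20% and 30%) the shift is −0.9 to +0.6. If the share were as high as 75%, with arms in adjacent weeks, the contrast would lie between 8.7 and 10.8 points.

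**Front-loaded response (extreme case).** Suppose the whole 18-point effect falls inside every open window, with s = 0.28.
- All windows open: control gains 0.28 × 0.98 × 0.8 × 18 = 3.95, standard 2.82 and COVID 2.42. COVID versus standard becomes 9.6 points (power 75%); standard versus control becomes 26.9.
- Only one message arm's window open: COVID versus standard shifts by +2.4 (COVID open) or −2.8 (standard open).

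**Two-week scheduling.** A 2-week window opened in week 3 closes by about week 5, before any MyChart message.

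**The case against.** The strongest reply is that the effect is small and may be absent. The overlap touches only the tail of the window and only MyChart families, and a visit must be both booked and completed in the days left. The 1100 may already omit MyChart families, or the MyChart trial may have started later than planned. This stands as a limit on size, but the documents do not say that either happened. The protocol's MyChart-account covariate does not answer the point: it is adjusted for only if the groups differ at baseline, and the overlap arises after randomization.

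Three stronger readings are tempting and are not supported:

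- **That the COVID arm is favored because week B follows week A.** The letters have no stated calendar order and the sequence is randomized. Even with the order known, the longer window and the smaller number of unbooked children pull in opposite directions.
- **That contamination could reach about 6 points.** A 70% MyChart share, a 30% response and 35% of it inside the window give 0.7 × 0.8 × 0.30 × 0.35 = 5.9 points. That is a gross gain in one arm, not a difference between arms. It also applies one group's response rate to all four messaged groups, and uses a share well above the 23-28% that the pools suggest.
- **That the COVID-vaccination outcomes are hit directly.** As described, MyChart messages carry the name only, or the last visit date and age. Any effect on vaccination runs through the visit.

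Nor does the overlap bias the MyChart trial's own comparison, because its new randomization balances earlier Televox exposure.

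**Conclusion.** The gap is real. As written, the plan lets a second randomized outreach into the 12-17 primary outcome, with exposure that differs by arm and a net direction that cannot be determined. Under an even spread of response and a 23-28% MyChart share, the shift in the COVID-versus-standard contrast is about 1 point or less against a planned 10. It could reach 2 to 3 points only if response were fully front-loaded and a single message arm's window were open. Message-versus-control stays near its planned 28 points and scheduling within 2 weeks is untouched.

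These sizes rest on assumed send days, an assumed equal MyChart share at both ages and assumed response timing, none of which the documents give. The point is worth correcting because the plan has power of just 80% for that contrast, but it does not threaten the trial's main message-versus-none conclusion.

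**What to change.** For any MyChart randomization still to come, add to its eligibility: *not randomized in a Televox trial whose 8-week outcome window is still open*. Alternatively, start MyChart for adolescents after the last 12-17 window closes, which is week 12 or later on this calendar. The cost is that some adolescents enter the MyChart trial later, in a pool of 1000 that is already below the 1465 needed. The protocol already allows extra MyChart replications to make up numbers.

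Excluding MyChart families from the 12-17 trial is less attractive: the pool of 1100 exceeds the required 1068 by only 32 (2.9%).

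The SAP describes the 12-17 trial in the past tense, with a study end of 8/5/21, so its enrolment can no longer be changed. If the MyChart trial has also run, compare MyChart message dates with each adolescent's Televox window, report the overlap by arm, and add a sensitivity analysis of the 12-17 primary outcome restricted to families without MyChart at baseline. That restriction preserves the randomized comparison, at the price of a smaller sample. Do not censor or drop only the re-randomized children: they are identified by not having responded, so removing them conditions on a post-randomization outcome. The work is one data linkage and one table.

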8. Community rates of COVID based on 7 day moving average.

Power/Sample Size

Personal Contacts (12-14 month & 4-year-olds) Trial:

We based our hypotheses (see table, below) on a systematic review's pooled estimates of effect size for automated messages and personalized calls finding 37% and 40% of children, respectively, completed immunizations.¹ Because of the significant cost involved in making personal contacts, the minimal difference in outcome that would make it worth the effort is high.

Hypotheses	% of children who receive MMR by 15 months of age	
	1 automated message sent	2 automated messages sent
0 personal attempts	20% ^C	35% ^B
1 personal attempt	50% ^A	65% ^{AB}

We calculated sample size needed per group to detect a difference for each of the contrasts below with alpha of 0.05 and power of 80%.

Contrast	Sample Size per Group
A vs C	36
B vs C	136
A vs. B	167
A vs. AB	167
B vs. AB	40
C vs. AB	16

To fully power the 2 X 2 factorial trial, we estimate needing 167 per group X 4 groups = 668 total subjects. There are currently 712 children eligible for the study. More will become eligible every month so we expect to far exceed the required sample size after 3 replications. If needed, we could increase the number of replications of the trial to reach the targeted sample size. We acknowledge that we are not powered to precisely estimate any interactions between interventions.

MyChart Trial:

In hypothesis testing for 0 message vs. 1 message vs. 2 messages, we will do the testing in a fixed sequence - test 2 messages vs. 0 message first, only if it is significant then test 2 messages vs. 1 message, thus the type I error rate of 0.05 is retained. Since the hypothesis testing of 2 messages vs. 0 message would be considered easier to achieve than the hypothesis testing of 2 messages vs. 1 message, the power analysis for this trial should be based on the design of (standard message vs. tailored message) by (1 message vs. 2 messages). We based our hypotheses (see table, below) on previous work indicating approximately 20% WCC appointment completion on automated text reminders. We anticipate that a tailored message increases the WCC appointment completion rate by another 10%.

Hypotheses		% of children complete WCC within 8 weeks

	No message	1 automated message sent	2 automated messages sent
Standard Message	2%	10% ^C	20% ^B
Tailored Message		20% ^A	30% ^{AB}

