For the Personal Contact (12-14 mo & 4 years old) trials, we will conduct intent-to-treat analyses using logistic regression models (without adjusting for covariates) for each of our three binary outcomes: completed appointment within 2 weeks, completed appointment within 8 weeks, receipt of MMR by 15 months of age or receipt of 2nd MMR by 3 months after randomization. We will do pair-wise comparison among the 4 groups and adjust p value of each comparison for multiplicity. If participants in the 4 groups differ on potential covariates, we will conduct additional analyses adjusted for these variables.

For the MyChart and Televox Trials (6-17 years old), we will conduct intent-to-treat analyses using logistic regression models (without adjusting for covariates) for each of the binary outcomes: scheduled appointment within 2 weeks, completed appointment within 8 weeks, receipt of 1st dose of COVID vaccination (age 12-17 years) within 8 weeks, family member receipt of COVID vaccination within 8 weeks. We will do pair-wise comparison among the treatment groups and adjust p value of each comparison for multiplicity. If participants differ in potential covariates across treatment groups, we will conduct additional analyses adjusted for these variables. We will explore non-inferiority analysis for comparison the two groups that are expected to have similar appointment scheduled and completion rate in the MyChart trial.

We will also conduct per-protocol analyses according to the interventions actually received by the participants, recognizing that actual intervention received could be different from initial randomized intervention. For example, a parent allocated to group A might schedule an appointment after receiving the automated message and therefore would not receive a personalized contact attempt. In addition, we may explore potential interaction between the two interventions as a secondary analysis. All analysis will be conducted using SAS version 9.4.

Duration

The study will begin upon IRB approval and continue through December 31, 2022. During this time, we will discuss the significance of data, potential future projects and dissemination of results.

Process of Obtaining Consent

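### In both Televox trials the two message scripts never share a contact week, so the script contrast cannot be separated from calendar week; the size is unknown and probably small for 8-week completion

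*Combined protocol and SAP*

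**What the plan says.** The schedule is in the protocol under MyChart and Televox Trials (6-17 years old). Children are randomized individually within clinic, but weeks are assigned to whole groups: "Groups will receive their assigned intervention in one of four successive weeks with the sequence randomly assigned (see table below".

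- **Televox 12-17:** "Low Tailored Message 2 automated tailored messages sent (e.g. Thu, Fri) (week A" against "COVID Tailored Message 2 automated messages sent (e.g. Thu, Fri) (week B".
- **Televox 6-11:** the low script is marked weeks C, C; the other arm reads "High Tailored Message 2 automated tailored messages sent (e.g. Thu, Fri) (weeks D, D".
- **MyChart:** both 1-message cells are in week A and both 2-message cells in week B, so standard and tailored messages share weeks.
- **Calendar:** "Weeks 1-3 = Televox Trial 12-17yo, Weeks 4-7 = Televox Trial 6-11yo, Weeks 8-10 = MyChart Trial".

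The protocol's covariate list includes two items that can change from week to week: "Number of days to 3rd next available appointment at patient's clinic at time their first automated message is sent" and "Community rates of COVID based on 7 day moving average".

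The protocol's Analysis section plans models "using logistic regression models (without adjusting for covariates) for each of the binary outcomes: scheduled appointment within 2 weeks" and the other outcomes. It adjusts pairwise p values for multiplicity and adds adjusted analyses if groups differ on covariates. SAP 2.3.2 compares the three 12-17 groups by logistic regression with no week term. The baseline list in SAP 2.3.1 has neither appointment access nor COVID rate.

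**The concern.** Low vs COVID and low vs high are the contrasts that set the Televox sample sizes (356 and 293 per group). If appointment access or community COVID activity differs between the two contact weeks, the difference enters the script comparison directly. A model that treats children as independent puts none of this uncertainty into the confidence interval. The COVID wording, or the tailoring, could then be credited with, or denied, an effect that belongs to the week.

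**Working it through.** **1. The plan's own figures.** Two-sided 0.05, power 80%, pooled variance: n = [1.96√(2p̄(1−p̄)) + 0.842√(p₁(1−p₁)+p₂(1−p₂))]² / (p₂−p₁)².

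- 30% vs 40% gives 355.9, stated 356.
- 20% vs 30% gives 293.2, stated 293.

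Both reproduce. They allow for binomial error only, with no week component.

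**2. Can a model separate script from week?** Take the two message arms, with columns for intercept, arm, week and two clinic terms.

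- 12-17 as tabled: rank 4 of 5. With each arm split over both weeks: 5 of 5.
- 6-11, if C, C and D, D mean two weeks per script: 6 of 7 as tabled, 7 of 7 when split.
- Access in place of week: 5 of 5, but 4 of 5 if access shifts equally at all clinics. It can therefore remove part of a week effect at best.
- One community COVID value per week in place of week: 4 of 5, so it is aliased with arm.

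**3. Size under a random week effect.** Let σ be the between-week SD (assumed), ρ the correlation between weeks and k the weeks per arm. V = 2p(1−p)/n is the variance the model sees, and W = 2σ²(1−ρ)/k is what it omits. Type I error = 2[1 − Φ(1.96√(V/(V+W)))].

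ρ is set to window overlap for adjacent weeks: 7 of 8 weeks (0.875) for completion and 1 of 2 (0.5) for scheduling. The same base rates are assumed for scheduling.

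Example, 12-17 with protocol inputs, σ = 2 points, ρ = 0.875: V = 2×0.30×0.70/356 = 0.001180; W = 2×0.0004×0.125 = 0.0001; 1.96√(0.001180/0.001280) = 1.882, which gives 6.0%.

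| Inputs | Completion, σ=1 | Completion, σ=2 | Scheduling, σ=1 | Scheduling, σ=2 |
|---|---|---|---|---|
| 12-17 protocol (30%, 356) | 5.2% | 6.0% | 6.0% | 9.0% |
| 12-17 SAP (20%, 859/3 ≈ 286) | 5.3% | 6.0% | 6.0% | 9.3% |
| 6-11, one week per script (20%, 293) | 5.3% | 6.1% | 6.1% | 9.4% |
| 6-11, two weeks per script | 5.1% | 5.5% | 5.5% | 7.2% |

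Simulation at σ = 2 with one week per script gives 6.0% to 6.2% and 9.1% to 9.5%. With arms split over shared weeks it gives 5.1% to 5.2%. Adjacency is itself assumed: if weeks A and B were two apart, 2-week windows would not overlap (ρ = 0), and 12-17 scheduling would be at about 7% (σ=1) or 13% (σ=2).

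**4. With multiplicity adjustment.** Under Bonferroni for three comparisons the threshold is 0.05/3 = 1.67%. At σ = 2 and one week per script, the rejection rate is about 2.2% for completion and 3.9% to 4.1% for scheduling.

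**5. Conditional on a fixed gap.** If the two weeks differ by 1, 2 or 3 points and the scripts do not, false positives are about 6%, 9% and 14% unadjusted, or about 2%, 4% and 6% to 7% under Bonferroni.

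**The case against.** The strongest reply has five parts.

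- **Random order.** It makes a week gap equally likely to favour either script beforehand. True, but 12-17 has one draw and no replication, so the realized gap remains.
- **Small effect on the sizing outcome.** This stands: 8-week windows one week apart share most of their calendar time.
- **Multiplicity adjustment.** It lowers the absolute error rate, and this also stands. However, the method is unnamed, a step-down procedure could test the last contrast at 5%, and the SAP does not repeat the adjustment.
- **Covariates.** They help only in part. Adjustment is additional and conditional, COVID rate is nearly aliased with arm, and SAP 2.3.1 omits access, although SAP 2.3.2 does not expressly exclude the protocol's list.
- **Week in the main model.** A contact-week term is undefined for the no-message arm, whose window starts at randomization. It cannot simply be added to the three-group model.

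A reader might infer that the script comparisons carry a known bias with 9% to 14% false positives. The documents do not support that: they give no week effect, and those rates need an assumed fixed gap and no multiplicity adjustment. A reader might also infer that MyChart is equally affected. Its Power/Sample Size text expects two replications, and the Personal Contacts table shows the week order changing between replications. MyChart standard vs tailored messages share weeks and are not affected.

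**Conclusion.** The confounding is complete for low vs COVID in 12-17. In 6-11, low and high never share a week, whichever way the C, C and D, D labels are read. It is milder and conditional for MyChart 1 vs 2 messages. The sample sizes are not wrong.

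The size cannot be derived from the documents. With an assumed week SD of 1 to 2 points and adjacent weeks, unadjusted type I error is about 5% to 6% for 8-week completion and about 6% to 10% for 2-week scheduling, and lower with multiplicity adjustment. This is worth correcting because the correction is cheap, not because a large distortion has been shown.

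**What to change.** **Trials or replications not yet sent.** In the MyChart and Televox schedule, randomize each message arm within clinic evenly across the same contact weeks, so that compared scripts, and MyChart 1 vs 2 messages, share every week. State how many weeks C, C and D, D mean. Compare message arms in a model restricted to those arms, with contact week as a stratum or covariate. Keep the full model, with the no-message group and without a week term, for comparisons with no message, or give control children a randomized index week.

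**Trials already sent.** This covers 12-17, given the SAP 2.2.1 end date of 8/5/21. It may cover 6-11 and MyChart: an 8-week window closing on 8/5/21 implies 12-17 messages by about 6/10/21, and consecutive week numbering would put week 10 seven weeks later, near the end of July 2021, before either document date. The protocol's Duration section runs to December 31, 2022, so this is not certain. Report each arm's contact dates and clinic-level appointment access, include access in the additional adjusted analysis, and state that the script contrast cannot be separated from contact week.

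**Cost.** Sample size, total messages and messages per week do not change. Two scripts are loaded in the same week, which needs a check that each child gets the assigned one. The message-arm model must be specified separately. For trials already sent, the cost is reporting and one covariate.

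### The 167 per group (668 total) for the Personal Contacts trial is sized on MMR by 15 months, which its 4-year-olds cannot newly reach, so 80% power is unsupported for the enrolled mix on the limiting 15-point contrasts

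*Combined protocol and SAP*

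**What the plan says.** The calculation stands in the protocol under Power/Sample Size, in the part headed "Personal Contacts (12-14 month & 4-year-olds) Trial". The SAP covers only the 12-17-year-old trial, so this is the only power statement for Personal Contacts.

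- **Planning rates.** The hypothesis table gives the percentage "of children who receive MMR by 15 months of age": 20% (C: one automated message, no personal contact), 35% (B: two messages, no contact), 50% (A: one message, one contact) and 65% (AB: two messages, one contact).
- **Sizes.** Six pairwise sizes follow, each for a "difference for each of the contrasts below with alpha of 0.05 and power of 80" percent. The largest is 167, for A vs B and A vs AB. Multiplied by four groups it gives 668, presented as enough to power the factorial trial in full.
- **Pool.** The target is compared with one undivided count: "There are currently 712 children eligible for the study".
- **Primary outcome.** Response variables and Analysis both define a composite. The Analysis wording is "receipt of MMR by 15 months of age or receipt of 2nd MMR by 3 months after randomization". The main model is unadjusted and pools both ages.
- **Eligibility.** Under Patient Population, the 12-14-month-olds must still lack their 12-month immunizations. A 4-year-old needs no recent well visit, but the second MMR dose need not be outstanding.

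**The concern.** A 4-year-old is long past 15 months, so outreach cannot change the event on which the sample size rests. What such a child can newly contribute is "receipt of 2nd MMR dose by 3 months after randomization". That is a different dose, at a different age and in a different window, and the protocol assumes neither a rate nor an effect for it. Because eligibility does not require the second dose to be outstanding, some 4-year-olds may enter unable to respond, which would dilute any difference between groups.

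The two contrasts that set 167 have no slack: they sit at 80% only if every child follows the table. If 4-year-olds respond less, a null result on A vs B or A vs AB could be read as coming from a trial with full power when it did not have it.

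**Working it through.** **Inputs.** Rates, alpha, power and 167 per group come from Power/Sample Size. The infant share f (infants meaning the 12-14-month-olds) and all second-dose rates are my assumptions, because the documents give none. Alpha is unadjusted two-sided 0.05, which reproduces the plan's figures.

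**Step 1: the plan's own sizes.** The formula is n = (1.960 + 0.842)² × [p1(1−p1) + p2(1−p2)] / (p1−p2)², with (1.960 + 0.842)² ≈ 7.849.

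| Contrast | Calculation | n | Stated |
|---|---|---|---|
| A vs C | 7.849 × 0.4100 / 0.0900 | 35.8 | 36 |
| B vs C | 7.849 × 0.3875 / 0.0225 | 135.2 | 136 |
| A vs B | 7.849 × 0.4775 / 0.0225 | 166.6 | 167 |
| A vs AB | 7.849 × 0.4775 / 0.0225 | 166.6 | 167 |
| B vs AB | 7.849 × 0.4550 / 0.0900 | 39.7 | 40 |
| C vs AB | 7.849 × 0.3875 / 0.2025 | 15.0 | 16 |

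All six reproduce after rounding up. There is no arithmetic error.

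**Step 2: the outcome in the table.** Only infants can contribute, so m = 167f per group. Power = Φ(0.15 / √(0.4775/m) − 1.96) for A vs B and A vs AB.

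- f = 1.0, m = 167: 80%
- f = 0.7, m ≈ 117: 65%
- f = 0.5, m = 83.5: 51%
- f = 0.3, m ≈ 50: 34%

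Holding 167 infants per group at f = 0.5 would take 167 / 0.5 × 4 = 1336 children.

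**Step 3: the composite outcome, A vs AB, 167 per group, f = 0.5.** Let 4-year-olds start at 50%, as the infants do, and gain d4. The pooled rates are 0.50 and 0.50 + 0.5 × 0.15 + 0.5 × d4.

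- d4 = 0.15: 0.500 vs 0.650, power 80%
- d4 = 0.075: 0.500 vs 0.6125, Φ(0.1125 / √(0.4873/167) − 1.96) = 55%
- d4 = 0: 0.500 vs 0.575, Φ(0.075 / √(0.4944/167) − 1.96) = 28%

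The base rate matters somewhat. With 4-year-olds starting at 5%, the same three gains give about 83%, 60% and 32%. Starting at 30%, they give 79%, 55% and 28%.

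**Step 4: the other contrasts at f = 0.5.** With infants analysed alone (83.5 per group), A vs C has 99% power, B vs AB 98% and C vs AB over 99%. All three are about 97% or more under either variance formula. B vs C, also a 15-point contrast, falls from 88% to 60%. If 4-year-olds instead stay in the pooled composite with no effect at all, the 30-point infant difference becomes 15 points. For 4-year-old base rates of 0 to 50%, power is then 96% down to 80% for A vs C and 89% down to 79% for B vs AB. C vs AB stays at about 99%.

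**The case against.** The strongest reply is that the primary outcome is the composite, which 4-year-olds can meet, and that infants-only power describes an analysis the protocol does not plan. That stands. A reader might infer from the label on the table that the enrolled sample lacks 80% power for its primary outcome. The documents do not show this. If 4-year-olds follow the table's rates, 668 gives about 80%. With a low base rate, even a gain just under 15 points is enough: half infants and 4-year-olds going from 5% to 19% gives pooled rates of 27.5% and 42%, and power of about 80%.

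A reader might also take the covariate rationale "visits are less frequent for children age 4 years" as the plan's admission that 4-year-olds respond less to outreach. It concerns visit frequency and says nothing about response. The smaller gains in the working are therefore illustrations, not findings.

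Two further points have weight. The contrasts that isolate personal contact at a fixed number of messages (A vs C, B vs AB) are much less exposed. And 668 is a floor: the protocol expects to go well beyond it and allows more replications. But no enrolment figure is given, and the stopping target was itself derived from one age group's outcome. At the 712 already eligible (178 per group), the zero-gain case in Step 3 rises only from 28% to 30%: Φ(0.075 / √(0.4944/178) − 1.96).

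**Conclusion.** The point holds as a mismatch between the outcome used for sizing and the population and outcome to which the size is applied. Two statements are firm. First, 668 children of mixed age do not give 80% power for MMR by 15 months on A vs B or A vs AB, because fewer than 167 per group can contribute. Second, nothing in the documents supports 80% for the composite on those two contrasts, since the second-dose rates and the age mix are both unstated.

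How far composite power falls, if it falls at all, is unknown. The range of 28% to 80% rests on assumed values: half infants, a 50% base rate in both ages, and 4-year-old gains of 0 to 15 points. The three larger contrasts keep high power among infants alone at that split. They would approach 80% only in the extreme case of no effect in 4-year-olds, and C vs AB not even then. All figures use unadjusted alpha; the planned multiplicity adjustment is a separate matter.

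**What to change.** Restate the Personal Contacts part of Power/Sample Size on the composite primary outcome:

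- Split the eligible count by age group, using the EHR report already run.
- State the assumed second-dose rates for 4-year-olds in each of the four groups, allowing for children whose second dose is already given.
- Report power at 668 for each of the six contrasts at that age mix, with infants-only power for MMR by 15 months as a supplement.
- Remove the claim of full power for any contrast below 80%.

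The cost is a recalculation and a wording change. The stated power may become less favourable for the 15-point contrasts. Restating it requires no additional children.
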